#### 12.5 *Payment:*

In phase II, providers who are randomized to the treatment arm will take part in a professional skills building workshop as part of the intervention condition. All costs associated with workshop participation including lodging will be covered by the study budget. In addition to these costs, participants of the workshop will be provided study compensation for completing the pre-workshop videos, and attending the in-person training (42 dollars / 300 RMB compensation for each participant). These compensation amounts have been deemed necessary by the local team members based on historic challenges of sustaining adequate attendance by providers who have many competing demands for their time. Immediately after the intervention, staff will conduct clinic visits to survey the provider participants. Both control and treatment arms participants who finish the follow-up survey will receive 50 RMB (about 7 USD) compensation.

Commented [KS1]: Add compensation for completing the intervention training.

SPs for the qualitative sub-study will receive 150 RMB (about 24 USD) for the first round of interviews and 50 RMB (about 7 USD) for the second round.

### 13.0 Withdrawal of Participants

#### 13.1 *Withdrawal Circumstances*

Any participant wishing to withdraw from the study for any reason is permitted to do so at any point in the study.

#### 13.2 *Withdrawal Procedures*

Once intention to withdraw or to be withdrawn has been confirmed, study staff will initiate discussion with participants about their wishes regarding retention of data they have already contributed to the study. Withdrawing participants will be offered a choice between having their data retained or discarded from the remainder of study proceedings. They will also be informed that aggregate information about the facility at which they work or about colleagues working at the same facility will still be used as part of the planned analysis.

#### 13.3 *Termination Procedures*

We do not anticipate many circumstances in which study investigators would need to terminate a participant from the study. Barring any harm to participants, termination may also be considered if participant continuation threatens

PROTOCOL TITLE: Standardized Patients to Address Intersectional Stigma  
VERSION DATE: 07/23/2019

successful implementation of the study. The most plausible scenario for which our team will be prepared are cases when a provider, suspecting a certain patient is an SP, may choose to confront the SP during an unannounced clinic visit. This would not directly harm the provider nor the SP, but may signal to the study team that the provider's participation may be jeopardizing the quality of care received by the provider's other patients. In such an event the SP and the co-PIs will discuss the episode and its possible effects on the participant and those around him/her. A final decisions around termination will be jointly made by the co-PI's, who may also consult the provider CAB for guidance in the matter if deemed necessary. As with withdrawal procedures, terminated participants will be offered a choice between having their data retained or discarded from the remainder of study proceedings. They will also be informed that aggregate information about the facility at which they work or about colleagues working at the same facility will still be used as part of the planned analysis.

## 14.0 Risks to Participants

### 14.1 *Foreseeable Risks:*

Provider participants in our study may be considered a group with a justified fear of negative consequences for not participating in the research. As in other professions, medicine in China is a relatively hierarchical field in which junior level physicians generally follow orders of their superiors. Therefore if a facility director has issued consent for his/her facility to take part in the study, some providers may sense unspoken pressure to take part in the study even if against their will. Some may fear retribution (e.g. pay cut, demotion) from their superiors for refusal to participate in research. To ensure that our providers are protected from either of these risks we have and will continue to take the precautions listed in Section 10.2.

An additional factor that may make our provider participants vulnerable is the fact that our study collects data on their behaviors including potentially discriminatory or stigmatizing behavior towards patients. If data on these adverse interactions are leaked, this could generate negative press for the provider or the facility and even form grounds for a medical malpractice suit.

Details on the measures to be taken to minimize these risks are detailed in Section 10.2.

Foreseeable risks to SPs taking part in the qualitative sub-study may include psychological duress experienced from recalling unpleasant experiences during their participation in this study or in recalling experiences of discrimination from their personal life.

### 14.2 *Reproduction Risks:*

N/A

### 14.3 *Risks to Others:*

PROTOCOL TITLE: Standardized Patients to Address Intersectional Stigma  
VERSION DATE: 07/23/2019

There is a possibility that providers working at facilities randomized to the control arm may perceive an inequity in their assignment and alter the quality of care they provide to their patients. To minimize this risk we have adopted the modified Zelen design in which participants randomized to the control arm are not informed of their assignment or that the study is a randomized trial. Conversely patients of providers randomized to the treatment arm may receive better-than-standard care quality as a result of their providers' awareness of the study objectives. This may ultimately result in an unintended *benefit* for these patients. To minimize the impact of such effects on the unbiased estimation of program impact, however, we are taking many precautions to mask the true objectives of the study from participants and rather describe it as generic research on "health services."

## 15.0 Incomplete Disclosure or Deception

### 15.1 *Incomplete Disclosure or Deception:*

In order to preserve the scientific validity of our main study outcome (stigma) and to minimize risk of unintended behavior change in the control group due to knowledge of the treatment condition, our consent procedures involved the two distinct forms of deception detailed below. Guided by the principles of respect for persons and beneficence from the Belmont Report, we centered our design on the goal of maintaining minimum necessary levels of deception and prioritizing participant well-being in all study procedures.

In order to preserve the integrity of our primary outcome measure—HIV and sexual stigma on the part of medical providers towards their patients—we have and will continue to abstain from any reference to stigma in all participant interactions. Instead, all reference to the study and its objectives has been and will continue to be couched in the language of generic research on "patient-centered care." The justification for this approach is to avoid alerting participants to the notion of healthcare stigma, which could induce altered behaviors under observation. Doing so would not only undermine our ability to observe and learn from typical clinical behaviors but would also interfere with our ability to conduct an unbiased evaluation of our stigma reduction intervention. In addition, SP visits to observe provider behaviors are only partially unannounced; that is, providers are informed of the time range during which an SP visit will happen but not of the exact day or which patient is an SP. The justification for this approach is to reduce risk of SP discovery by providers and maximize our ability as researchers to observe true clinical behaviors. Providers are given opportunities at the end of the study to guess which patients may have been SPs in order to test the validity of our stigma measure. Past uses of the unannounced SP visit model by co-PI [name] have reported discovery rates of 7%.

A second instance of deception in this study is the masking of the randomized nature of the study to facilities and providers in the control arm. This approach, the modified Zelen design, can be considered ethical in instances when the intervention is not considered to be therapeutic or potentially life-saving. It can be also be considered justifiable if used to mitigate inadvertent altering of behaviors by individuals in the control arm due to their awareness of the treatment condition. Moreover if these altered behaviors have the potential to disadvantage their patients in terms of the quality of care they receive during the study, the

PROTOCOL TITLE: Standardized Patients to Address Intersectional Stigma  
VERSION DATE: 07/23/2019

modified Zelen is even further justified. At the close of the study we will refrain from revealing the randomized nature of the study in order to preserve ideal conditions an anticipation of a fully powered RCT to follow this pilot study. In the event that control arm providers learn of the intervention (a hybrid professional skills building workshop) through their personal networks and confront study investigators or coordinators, the event will be explained to them as an experimental training that the GDCDC is piloting for potential future scale up.

## **16.0 Potential Benefits to Participants**

Provider participants randomized to the treatment arm will benefit from the opportunity to take part in the stigma reduction intervention. Those randomized to the control arm will not access this benefit. However they may gain indirect benefits in the form of contributing the development and evaluation of an intervention to reduce the incidence of stigmatizing and discriminatory behavior towards PLHA and MSM in Chinese medical settings. If found effective, the intervention developed in the course of this study may be adopted by provincial policy makers (our co-investigators at the GDCDC) and incorporated into routinized clinical training throughout the provincial network of DV practices. The model for measuring and addressing enacted healthcare stigma developed in the course of this study will also be documented and disseminated with the intention for it to be replicated in other settings, particularly in low/middle-income settings that bear the greatest burden of HIV worldwide and where stigma is most severe.

SPs taking part in our qualitative sub-study may benefit from the interviews by having an opportunity to share their personal experiences with the study team or air any grievances about study conduct.

## **17.0 Data Management**

### **17.1 Data Analysis Plan:**

The primary goal of the study is to estimate the impact of healthcare stigma—in particular stigma directed at patients living with HIV (HIV stigma), patients who have same sex behaviors (homophobia), and patients with both attributes (intersectional stigma) on the quality of sexual healthcare they receive. Stigma is quantified as the difference in the mean healthcare quality index across the four case scenarios. Patterns of stigma occurrence are also assessed by stratifying results across key attributes such as tier of care (e.g. county hospital versus township clinic), rural/urban region, provider sex, and provider professional rank in order to illuminate provider subgroups of interest to inform tailored intervention design. A secondary analytical goal of this study is to assess the preliminary effect of the intervention on healthcare quality by comparing the same healthcare quality index across treatment arms. Details in the power analysis (section 17.2) and statistical analysis (section 17.3) sections are described separately for these two goals.

For the qualitative sub-study analysis, data from debrief session conducted with SPs following each clinic visits will be transcribed and translated into English by study staff and spot checked by the co-PIs for transcription accuracy by bilingual

PROTOCOL TITLE: Standardized Patients to Address Intersectional Stigma  
VERSION DATE: 07/23/2019

study staff. Co-PIs will oversee analysis by study staff including coding of transcripts and identification and interpretation of emergent themes.

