In the final step of the initial preparatory phase of this project, we conducted a preliminary and descriptive analysis of the SP-collected baseline clinic visits in order to characterize the nature and patterns of enacted healthcare stigma towards PLWH and MSM. Results quantified the amount of HIV and sexual stigma observed in study clinics (further details of the outcome in Section 3.0), and also stratified results by broadly descriptive characteristics such as age, sex, and rank of provider. These results were shared in Return of Results (RoR) sessions with members of community advisory boards (CABs), one made up of MSM and the other of providers through separate share back sessions. We convened meetings with CAB members to solicit their insights about drivers of provider behaviors observed in their community. The team incorporated CAB feedback to develop the intervention, a stigma reduction training program for provider participants employed at clinics randomized to the treatment arm. Details of the final design were informed by feedback from study team members and each of the two CABs, the overall structure consists of didactic content as well as experiential learning using simulation-and-feedback sessions with trained SPs. We may re-consult our CABs at later stages of the design for iterative feedback on any adjustments made to the intervention design.

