## 11.0 Number of Participants

### 11.1 *Number of Participants to be Consented:*

To demonstrate the preliminary effectiveness of the intervention we recruited approximately 20 facilities within which an estimated 8 eligible providers work. For the baseline visits a total of 160 unannounced SP visits were made, or about 8 visits per clinic. Given the nature of patient intake procedures at outpatients facilities of the type that our SPs will visit, we were unable to control which of the consented providers in a given facility consented to SP visits. It is therefore possible that some consented providers in these clinics will never receive an unannounced SP visit, while others may receive multiple visits.

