#### 17.2 Power Analysis:

**Stigma Quantification:** The primary objective of this pilot study is to estimate the extent to which stigma towards PLWH (HIV stigma) and towards MSM (homophobia) contribute to the deterioration of healthcare quality relative to straight people without HIV. A total sample size of 160 standardized patient (SP) interactions would provide 80% power (alpha=0.05) to detect a minimum effect size of 0.18 standard deviation. This calculation is conservative in that it does not account for blocked randomization of the SP cases within practices, which will lend additional power to each comparison. Two-sided tests will be needed to detect differences across the four case scenarios in order to separately quantify HIV, sexual, and intersectional stigma, for which the same assumptions will provide the same amount of power to identify a minimum effect size of 0.17 standard deviation between any 2 pairwise comparisons of scenarios. As recruitment will take place at the clinic level, the number of participants that will be needed to be recruited to the study will depend on estimates of the average numbers of eligible providers that our team can reasonably expect to recruit at each clinic. Preliminary data suggest that clinics in our study region employ an average of 5 eligible providers, of whom we conservatively expect to recruit 70% or 3.5 per clinic. Each provider will receive 3 unannounced visits from a standardized patient, yielding a final estimated pool of 56 providers for this study.

**Preliminary intervention effects:** A secondary goal of the RCT is to estimate the preliminary effect of the intervention on quality of care index observed by SPs. Though this is only a secondary goal, we determine that it is plausible that the target enrollment of 20 clinics randomly allocated to treatment and control in a 1:1 manner could yield sufficient power to detect reasonably small effects on the primary outcome measure. That is, with an alpha level of 0.05 for a one-sided test, an intra-cluster coefficient of 0.07, and a baseline prevalence of standardized quality of care index (with mean of 0 and standard deviation of 1), a sample size of 160 SP clinic visits (8 visits per clinic on average) would provide 80% power to detect a reduction in EOC scores due to the intervention as small as 0.17 standard deviations.

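### Section 17.1 looks for provider subgroups by stratifying the stigma results, but nothing in the plan estimates whether stigma differs between strata

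*Combined protocol and SAP*

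**What the plan says.** Section 17.1 defines stigma as the difference in mean quality index between the four scripts, then adds: "Patterns of stigma occurrence are also assessed by stratifying results across key attributes such as tier of care". The other attributes named are urban or rural location, provider sex and provider rank. The list is open-ended. The stated aim is "in order to illuminate provider subgroups of interest to inform tailored intervention design".

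Section 2.1 reports that the baseline analysis "stratified results by broadly descriptive characteristics such as age, sex, and rank of provider", and describes that analysis as preliminary and descriptive.

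Section 17.1 refers the reader to 17.2 and 17.3 for detail. Section 17.2 gives no power for subgroups. The stigma model in 17.3 contains HIV, MSM, their product, and fixed effects for facility and SP, with no product of script and provider or clinic attribute. Section 17.3 does use such products for one other question: whether stigma differs by trial arm is answered by interacting arm with script type.

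**The concern.** Asking which providers stigmatise more is asking whether the script gap differs between strata. Separate estimates for each stratum do not answer that. Two noisy gaps will differ even when the true gaps are equal, and a reader shown them side by side has no interval for the difference.

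At stake is what the report says about provider subgroups, and what later planning takes from it. Sections 7.0 and 15.1 look ahead to a full-scale trial, and section 16.0 to possible adoption in provincial training. An apparent pattern by rank or tier could shape that work although it is only sampling error.

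**Working it through.** **Inputs from the documents**
- Visits: "For the baseline visits a total of 160 unannounced SP visits were made, or about 8 visits per clinic" (11.1).
- Four scripts, balanced by design (12.1), so 160/4 = 40 visits per script.
- Tests between scripts: "Two-sided tests will be needed to detect differences across the four case scenarios" (17.2).
- Outcome scale: "standardized quality of care index (with mean of 0 and standard deviation of 1" (17.2, given there for the intervention comparison).

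**Assumptions, not in the documents**
- A two-level attribute splitting the visits evenly: 40/2 = 20 visits per script per stratum.
- SD 1, independent visits, no fixed effects.

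**The plan's own detectable effects.** Section 17.2 says 160 interactions "would provide 80% power (alpha=0.05) to detect a minimum effect size of 0.18 standard deviation", and gives a "minimum effect size of 0.17 standard deviation between any 2 pairwise comparisons of scenarios". With (1.960 + 0.842) × √(1/n₁ + 1/n₂):
- 80 v 80: 2.802 × √(2/80) = 0.443 SD.
- 40 v 40: 2.802 × √(2/40) = 0.626 SD.

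Neither stated figure is reproduced from the stated inputs. They are used below only as the plan's reference values.

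**Difference between two stratum gaps**
- One stratum's gap: variance 1/20 + 1/20 = 0.10.
- Difference of two such gaps: SE = √(0.10 + 0.10) = 0.447 SD.
- With equal true gaps, the mean absolute difference is 0.447 × √(2/π) = 0.36 SD.
- P(difference ≥ 0.5 SD) = 2[1 − Φ(0.5/0.447)] = 2[1 − Φ(1.118)] = 26%.
- P(difference ≥ 0.18 SD) = 2[1 − Φ(0.402)] = 69%.

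These figures do not depend on how large the common gap is, or on any significance rule. An uneven split is worse: at 30/10 the SE is √(2/30 + 2/10) = 0.516 SD. If facility effects remove a share of variance equal to the 0.07 intra-cluster coefficient in 17.2, the SE falls only to 0.447 × √0.93 = 0.431 SD.

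**If strata were judged by within-stratum significance.** Let p be the power of a two-sided 5% t-test at 20 v 20. With the same true gap in both strata, P(exactly one significant) = 2p(1 − p):

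| Common true gap (SD) | p | Exactly one significant |
|---|---|---|
| 0 | 0.050 | 9.5% |
| 0.17 | 0.082 | 15.1% |
| 0.18 | 0.086 | 15.7% |
| 0.3 | 0.152 | 25.8% |
| 0.5 | 0.338 | 44.7% |
| 0.626 | 0.488 | 50.0% |
| 0.8 | 0.693 | 42.5% |
| 1.0 | 0.869 | 22.8% |

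A simulation of 100,000 trials gave 44.6% at 0.5 SD.

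**Direct test of the difference.** In the same simulation, at common gaps from 0 to 0.626 SD, the interaction test rejected 4.8% to 5.1% of the time. Its 80%-power threshold is 2.802 × 0.447 = 1.25 SD. Four attributes by three script contrasts is 12 tests; if they were independent, the chance of at least one false positive would be 1 − 0.95¹² = 46%.

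**The case against.** The strongest reply is that this is description. Section 2.1 calls the baseline work preliminary and descriptive, section 5.1 calls the study a pilot, and no section sets a threshold or says that significance in one stratum and not the other will be read as a difference. That is correct, so the last column of the table shows what such a reading would produce, not what the plan prescribes. It does not remove the point: 17.1 attaches a comparative purpose to the strata, and the 26% figure needs no significance rule.

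A second reply is that the strata change nothing in this trial. A reader might infer that the plan uses the subgroup results to decide whom to target. The documents do not support that. Section 2.1 gives the training to every enrolled provider in treatment-arm clinics, and sections 4.1 and 5.2 describe one common curriculum. Section 1.1 says the preparatory work is complete and has already informed the design. This reply stands. What remains open is how the strata are reported and what later planning draws from them.

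**Conclusion.** The point holds as one about method: subgroups meant to inform tailoring are to be found by stratification, and the between-stratum difference in stigma is never estimated. Under the stated assumptions that difference has an SE of about 0.45 SD, so equal true stigma would show a difference of 0.5 SD or more about 26% of the time.

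A reader might also infer that 20 v 20 visits by itself yields a false subgroup difference about 45% of the time. It does not. That figure needs a common true gap of 0.5 SD, an even split and the significant-in-one-stratum rule, none of which is in the documents. Across common gaps of 0 to 1 SD the rate runs from about 10% to 50%, and at the plan's own 0.17-0.18 SD it is 15-16%. Here a false difference means equal stigma in both strata, not an absence of stigma.

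**What to change.** For each attribute, fit the 17.3 stigma model plus the attribute's products with HIV, MSM and HIV*MSM. The third product is needed to cover intersectional stigma. Add the attribute's main effect only for provider-level attributes (sex, rank); the facility fixed effects absorb tier and location, whose products with script remain estimable. An attribute with more than two levels needs a set of products for each non-reference level.

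Report the between-stratum difference with its 95% interval as the evidence for a subgroup difference, and show stratum estimates only beside it. Label all of these analyses exploratory, without multiplicity control.

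The cost is a paragraph of SAP text and four extra model fits. The real downside is precision. A pairwise script contrast has 80% power only for a between-stratum difference of about 1.25 SD, and the HIV*MSM product, which uses four script means per stratum, needs about 1.25 × √2 = 1.77 SD. Fewer subgroup statements will be possible. The change affects reporting and later trial planning, not the intervention already designed.

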### 3.0 Study Endpoints/Events/Outcomes

#### 3.1 Primary Endpoint/Event/Outcome

Our primary endpoint of the RCT phase of the study will be the quality of healthcare received by SPs in each clinical encounter with an enrolled provider. As a measure of the quality of healthcare provided in each interaction between physicians and standardized patients, we will create an index using 38 items from the structured post-interaction survey questionnaire administered to SPs following each unannounced visit. Individual items will be combined into a global index,  $\bar{s}_i$ , which is calculated as a weighted average of all 38 items, for which weights are calculated as the sum of its row entries in the inverted covariance matrix as follows:

$$\bar{s}_i = (1' \hat{\Sigma}^{-1} 1)^{-1} (1' \hat{\Sigma}^{-1} y_i)$$

where 1 is a column vector of 1s,  $\hat{\Sigma}^{-1}$  is the inverted covariance matrix, and  $y_i$  is a column vector of all items for individual  $i$ .

Using the analysis approach presented in section 17.3, we will estimate the impact of the intervention on the extent to stigma faced by SPs when presenting as MSM or HIV infected patients relative to the "standard" care experienced by the referent case scenarios of a straight, HIV uninfected man.

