The ITT impacts reflect the effect of physicians being *offered* an opportunity to participate in training, not the causal effect of training itself. We therefore also estimate the effect of participating in training using the model

$$\theta_{idc} = \pi_0 + \pi_1 A_{dc} + \pi_2 \bar{\theta}_{dc(t-1)} + \varphi X_{ic} + \nu_{idc}$$

where  $A_{dc}$  is a measure of whether or not doctor  $d$  in clinic  $c$  attends the training and other variables are defined as above. We fit this equation by two-stage least squares (2sls) using the following first-stage equation:

$$A_{dc} = \delta_0 + \delta_1 T_c + \delta_2 \bar{\theta}_{dc(t-1)} + \zeta X_{ic} + \mu_{idc}$$

where the excluded instrument is the treatment assignment of doctor  $d$ 's clinic,  $T_c$ . We interpret the coefficient  $\pi_1$  as the local average treatment effect, or LATE, of participating in training on the quality of care provided.

While the analysis outlined above provides estimates of the effect of the training (or offer of training) on the quality of care provided to SPs presenting with cases of presumptive syphilis, the goal is to estimate the effect of the training on *enacted stigma*. That is, rather than the overall effect on the level of healthcare quality, we are primarily concerned with observing how the training affects the difference in the quality of care received by patients presenting as MSM or HIV-positive vs. those not, all else equal. Our two levels of randomization (SP-doctor interactions disease script types and clinics to treatment or control) allow us to estimate the causal effect of training offer (or participation) by estimating regressions analogous to the above, but interacting the dummy clinic treatment allocation with dummy variables for each SP script type. For ITT effects, we estimate

$$\theta_{idc} = \alpha_0 + \alpha_1 T_c + \alpha_{11} T_c \times V^{HIV+,MSM-} + \alpha_{12} T_c \times V^{HIV-,MSM+} + \alpha_{13} T_c \times V^{HIV+,MSM+} + \alpha_2 \bar{\theta}_{dc(t-1)} + \gamma \Gamma_{ic} + \varepsilon_{idc}$$

Where  $V$  are dummy variables for three of the four script variations (leaving out the HIV-, MSM- variation).  $\Gamma_{ic}$  is a vector of SP fixed effects. The coefficients  $\alpha_{11}$ – $\alpha_{13}$  represent the effect of training offer on the *difference* in healthcare quality provided

PROTOCOL TITLE: Standardized Patients to Address Intersectional Stigma  
VERSION DATE: 07/23/2019

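### The RCT target is ranked inconsistently across sections, and the 0.17 SD detectable effect fits neither the care-quality level nor the stigma gap by arm

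*Combined protocol and SAP*

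**What the plan says.** Three different quantities are given first place in the current text.

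- **Stigma gap by arm.** Section 3.1 opens with "Our primary endpoint of the RCT phase of the study will be the quality of healthcare received by SPs in each clinical encounter", then says how that index will be used: "we will estimate the impact of the intervention on the extent to stigma faced by SPs when presenting as MSM or HIV infected patients". The straight, HIV-uninfected script is the reference. After the level models, 17.3 says that "rather than the overall effect on the level of healthcare quality, we are primarily concerned with observing how the training affects the difference" in care between scripts, and sets up three treatment-by-script coefficients, alpha_11 to alpha_13.
- **Size of stigma, with no arm comparison.** Section 17.1 states "The primary goal of the study is to estimate the impact of healthcare stigma", and 17.2 repeats that ranking. Section 15.1 refers to the "primary outcome measure—HIV and sexual stigma on the part of medical providers".
- **Level of care quality by arm.** Section 17.1 calls this secondary: "A secondary analytical goal of this study is to assess the preliminary effect of the intervention on healthcare quality". Section 17.2 also calls it a secondary goal, of the RCT itself. Section 17.3 nevertheless presents beta_1, the arm difference in the index with script type as a covariate, as the main ITT impact and the coefficient of interest.

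The power statement for the intervention sets up a two-arm comparison of the quality index, but concludes that the design "would provide 80% power to detect a reduction in EOC scores due to the intervention as small as 0.17 standard deviations". EOC is erosion of care in the abbreviation list, and 17.3 uses erosion for the script gaps.

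**The concern.** Someone working from 3.1 and someone working from 17.1 would run different leading analyses of the same trial, and the two can disagree. The training covers clinical diagnosis and management of common STIs (4.1, 5.2), and the checklist scores guideline adherence, conduct and communication (5.2). Care could therefore improve equally for all four scripts. The level effect would then be positive and the stigma effect zero.

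The power statement adds to this. Its wording suggests sensitivity to a change in stigma, while its inputs belong to a comparison of levels, and no detectable effect is clearly given for the gap by arm.

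The gap is spread over three coefficients with no rule for how they are judged together. The results bear on possible adoption by provincial policy makers (16.0) and on a later full-scale trial (7.0, 15.1), so the target matters even in a pilot.

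**Working it through.** **Inputs from 17.2 and 12.1.** 20 clinics allocated 1:1; 160 visits, 8 per clinic on average; SD 1; ICC 0.07; alpha 0.05 one-sided; 80% power; four scripts balanced across clinics. Assumed: 80 visits per arm and 20 per script per arm, no covariate gain, no losses. Multipliers: 1.645 + 0.842 = 2.486 one-sided; 1.960 + 0.842 = 2.802 two-sided.

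**1. The plan's figure, read as a level effect.**
- Design effect = 1 + (8 − 1) × 0.07 = 1.49.
- SE = sqrt(1.49 × 2/80) = 0.193.
- Detectable effect = 2.486 × 0.193 = 0.48 SD one-sided; 2.802 × 0.193 = 0.54 two-sided.
- Ignoring clustering, one-sided: 2.486 × sqrt(2/80) = 0.39.

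The stated 0.17 SD is not reproduced. Power at 0.17 is about 22% one-sided. To reach 0.17, the variance would have to shrink to (0.17/0.48)² ≈ 0.125 of its size, so covariates would have to explain about 87%. The plan gives no such figure.

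**2. The same inputs, read as the stigma gap by arm.** If clinic effects cancel within clinic, the residual variance is 1 − 0.07 = 0.93.
- One coefficient: SE = sqrt(4 × 0.93/20) = 0.431. Detectable effect = 1.07 SD one-sided, 1.21 two-sided. Power for a 0.17 SD change is about 11% one-sided, 6% two-sided.
- Average of the three: SE = sqrt(0.93 × 2 × (1/20 + 1/60)) = 0.352. Detectable effect = 0.88 one-sided, 0.99 two-sided.

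**3. Can the targets diverge?** In a simulation (2,000 runs, cluster-robust SE, t with 19 df), all scripts gained 0.5 SD in the trained arm and the stigma gaps were equal in both arms. beta_1 was significant in about 80% of runs one-sided (70% two-sided). Each treatment-by-script term, with script main effects included, was significant in about 5%.

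**4. The interaction equation as printed.** It contains T, the three T × script terms, the baseline mean and Gamma, and Gamma is defined as SP fixed effects only. Without script main effects, control visits share one intercept whatever the script. Setting SP effects and baseline aside, alpha_11 is then the trained-arm mean for that script minus the trained-arm referent mean. That is the gap in one arm, not the change in gap between arms. In the simulation, with assumed gaps of −0.3, −0.3 and −0.5 SD equal in both arms, the printed form returned on average about −0.3, −0.3 and −0.5 where the right answer is 0.

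**5. Three unadjusted tests.** The three contrasts share a referent, so with equal cells they correlate at 0.5. Three two-sided 5% tests then carry about a 12.5% chance of at least one false positive. Independence would give 1 − 0.95³ = 14%.

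**The case against.** A reader might infer that the plan intends to report a general quality gain as stigma reduction. The text does not support that. Section 17.3 says in terms that the level is not its main concern and specifies models for the gap; 17.1 labels the arm comparison as an effect on healthcare quality; and no section defines success. A uniform gain reported under that label would be true. This defence stands.

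Part of the conflict may be scope, because 17.1 speaks of the whole study and 3.1 of the RCT phase. That helps only partly, since 17.2 also calls the intervention effect a secondary goal of the RCT. Likewise, *main* in 17.3 may only separate ITT from the effect of attending, which follows at once. That reading is fair, but the text leaves it to the reader.

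A reader might also infer that the three coefficients must be collapsed into one average. The documents do not require it: 17.1 and 17.2 want HIV, sexual and intersectional stigma quantified separately, and an average can hide opposing effects.

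The missing script main effects may be a slip of notation, since 17.3 calls the interaction models analogous to the earlier ones, which include script effects. Finally, this is a pilot of preliminary effectiveness. That excuses low power and softens the need for strict multiplicity control. It does not excuse an unclear target or a detectable effect that its own inputs do not give.

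**Conclusion.** The point holds as an inconsistency to be resolved. Sections 3.1, 15.1, 17.1, 17.2 and 17.3 rank the RCT targets differently, and the 0.17 SD figure is worded for one target and built on inputs for another. It matches neither: one-sided, about 0.48 SD for the level, 1.07 for each gap coefficient and 0.88 for their average (two-sided 0.54, 1.21 and 0.99). The inconsistency of targets does not depend on these figures. The figures rest on SD 1, ICC 0.07, balanced scripts, clinic effects cancelling within clinic for the gap, and no covariate gain; a strong baseline covariate would lower them. Fitted as printed, the interaction equation would not isolate the change in stigma gap. Calling a general quality gain a stigma effect remains an open risk, not something the plan announces.

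**What to change.** - In 3.1, 15.1, 17.1, 17.2 and 17.3, state in the same words that the RCT-phase target is the treatment-by-script effect (alpha_11 to alpha_13), as 3.1 and the later part of 17.3 already imply. Label beta_1 as an effect on general care quality.
- Write the script main effects explicitly into the interaction equation in 17.3.
- In 17.2, replace the 0.17 SD erosion-of-care figure with two detectable effects, one for the level and one for the gap, and state the assumptions, including any variance the covariates are expected to explain.
- Pre-specify how the three coefficients are judged: a joint test, a multiplicity adjustment, or a one-degree-of-freedom average as one option. Report all three separately in any case.

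The cost is wording, one corrected equation and a short power table, with no new visits or data. The downside is that the stated detectable effect becomes visibly less favourable.
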